3.3. Dose Escalation and Stopping Rules

Dose escalation stopping rules will be used to determine whether the maximal tolerated dose has been attained. Dose escalation may be stopped if it is determined that the dose or dose regimen is deemed not to be tolerable. This decision will be made after a discussion takes place between the Pfizer study team and the investigator(s). The Pfizer study team may not overrule the Investigators' decision to stop dose escalation. If dose escalation is stopped due to any of these findings, additional cohorts may receive the same or lower doses of the investigational compound. Additional subjects may be added at a dose level to further evaluate safety and/or tolerability after discussions between the Pfizer study team and the investigators.

Single Ascending Dose Portion (n=8; 6 active treatment and 2 placebo)

Dose escalation will be terminated based on the following criteria:

- Two or more subjects receiving PF-06293620 drug (but not placebo subjects) develop similar clinically significant laboratory, ECG or vital signs abnormalities, or severe AEs in the same organ class, indicating dose-limiting toxicity as outlined in

Table 3 (Exception: dose escalation will be terminated if one (1) subject experiences ≥ 2 hypoglycemic events of Common Terminology Criteria for Adverse Events (CTCAE) Grade ≥ 3 which do not meet SAE criteria; see [Table 7](#)).

- It is determined that the dose is deemed intolerable. This decision will be made following discussions between the Study Team and the Investigator.

Other findings that, at the discretion of the Study Team and Investigator, indicate that dose escalation should be halted.

In the single dose cohorts, for any treatment-related serious adverse event (SAE), the subject will continue with the safety assessments until completion of the study.

Progression to the next dose will occur if the last dose was well tolerated and after satisfactory review of the available safety data.

Multiple Ascending Dose Portion (n= 8 PF-06293620 drug :2 PBO)

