For dose escalation, the decision to proceed to a higher dose will be made by the Pfizer study team and the Investigators after review of the available safety and tolerability data after 80% of the subjects in the previous cohort have received one dose and have been followed for 14 days post first dose. Enrollment in the previous cohort must be completed before initiating enrollment in a new cohort. If ≤ 2 subjects in a cohort discontinues the study prior to reaching Day 15, for reasons other than safety (eg, withdraw of consent), the subject(s) will be included in the dose escalation data review and do/does not need to be replaced for the purposes of determining dose escalation. The order of MAD regimen cohorts may change depending on the ongoing review of safety/PK data but at no time will doses be administered that exceed the PK exposure determined in the SAD portion. Dose escalation will be terminated based on the following criteria:

- Two (2) or more subjects receiving PF-06293620 drug (but not placebo subjects) develop similar clinically significant laboratory, ECG or vital signs abnormalities, or severe AEs in the same organ class, indicating dose-limiting toxicity as outlined in [Table 3](#) (Exception: dose escalation will be terminated if one (1) subject experiences ≥ 2 hypoglycemic events of CTCAE Grade ≥ 3 which do not meet SAE criteria; see [Table 7](#)).
- The limit of safety and/or tolerability has been reached.
- If dose escalation in the single ascending dose is terminated AND the exposure of the dose cohort in the multiple ascending dose portion is equal to or higher than the exposure of the dose determined to be the MTD after the single doses.

Dose Interruption

- If ALT or AST are increased $\geq 3 \times$ ULN, ALT and AST will be monitored at least weekly. If ALT or AST continues to rise ≥ 3 to $\leq 5 \times$ ULN prior to the next dose, the investigator and Sponsor will review the subject's clinical data prior to administering the next dose and dosing may be interrupted.
- Dosing will be interrupted in individual subjects when the following occurs:
 - a. Serum AST or ALT are increased to $>5 \times$ ULN (CTCAE Grade ≥ 3); confirmed within 7 days (by both local and central labs).
 - b. Confirm creatine kinase (CK) WNL and source of enzyme elevation is not muscle related.

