3.3.1. Toxicity Criteria

Table 7. Toxicity Criteria

Parameter	Definition ¹
Serious adverse event	Serious adverse event;
Increased liver transaminases ²	Serum AST ³ and/or ALT ⁴ are both increased to $>5 \times \text{ULN}^5$ (CTCAE ⁶ Grade ≥ 3);
Increased direct bilirubin ² (in absence of ALT/AST elevations)	Adapted from CTCAE ⁶ Grade ≥ 2 ;
Hypoglycemia	One (1) subject experiences ≥ 2 hypoglycemic events of <40 mg/dL (CTCAE ⁶ Grade ≥ 3) which do not meet SAE criteria;
Pancreatitis	Severe pain, vomiting; medical intervention indicated (CTCAE ⁶ Grade ≥ 3);
Decreased platelet count ²	Thrombocytopenia to $<100,000/\mu\text{L}$ [$<100 \times 10^9/\text{L}$];
Hypertriglyceridemia ²	>1000 mg/dL (CTCAE ⁶ Grade ≥ 4);
Increased serum creatinine ²	Serum creatinine to $2.2 \times \text{ULN}^5$ (CTCAE ⁶ Grade ≥ 3);
Diarrhea, enteritis or nausea	Increase of >6 stools/day over baseline; incontinence; hospitalization indicated; inadequate oral caloric or fluid intake (CTCAE ⁶ Grade ≥ 3);
ECG changes from baseline	Clinically significant ECG change from baseline including but not limited to interval changes (eg, PR, QTcF), ST-T wave changes, appearance of Q waves, atrial or ventricular rhythm abnormality, QRS axis deviation or ventricular conduction defect associated with clinical symptoms;
Prolongation of QT _c F interval ^{2,7}	QT _c F >500 msec (ie, CTCAE ⁶ Grade ≥ 3) or increase from baseline of ≥ 60 msec;
Unspecified	If considered appropriate by the medical monitor and investigator.

1. Unless considered to be unrelated to study medication by Investigator and Sponsor.
 2. To be confirmed by a repeat test.
 3. AST = aspartate aminotransferase.
 4. ALT = alanine aminotransferase.
 5. ULN = upper limit of normal reference range of the clinical laboratory.
 6. CTCAE = Common Terminology Criteria for Adverse Events.
 7. QT_cF = QT interval (Fridericia's correction).

In the event that a subject develops any of the toxicities outlined in Table 7, the subject will be followed until resolution and/or referred to an appropriate specialist

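### The one-subject hypoglycaemia stop leaves out serious events, and the Table 7 liver row contradicts itself on whether one raised enzyme is enough

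*Protocol*

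**What the plan says.** **General rule.** Protocol section 3.3 makes termination of escalation mandatory on listed criteria. The MAD version of the main one is "Two (2) or more subjects receiving PF-06293620 drug (but not placebo subjects) develop similar clinically significant laboratory, ECG or vital signs abnormalities", or severe adverse events within one organ class, where these indicate dose-limiting toxicity. The SAD version is equivalent. Both bullets point to Table 3 for the toxicities, but Table 3 holds SAD doses and safety margins. The criteria are in Table 7 (section 3.3.1).

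**One-subject exception.** In both parts, "dose escalation will be terminated if one (1) subject experiences" two or more hypoglycaemic events of CTCAE Grade 3 or higher, limited to events "which do not meet SAE criteria". The Table 7 hypoglycaemia row repeats the limit and sets the glucose level at below 40 mg/dL.

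**Serious events.** Table 7 has a serious adverse event row with no one-subject trigger. For SAD cohorts, section 3.3 says that "for any treatment-related serious adverse event (SAE), the subject will continue with the safety assessments until completion of the study". It does not say that one such event stops escalation.

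**Review before escalation.** For SAD, "Progression to the next dose will occur if the last dose was well tolerated and after satisfactory review of the available safety data". For MAD, "the decision to proceed to a higher dose will be made by the Pfizer study team and the Investigators" after review of safety and tolerability data.

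**Liver.** The Table 7 row requires that AST 'and/or' ALT "are both increased to" more than 5xULN, labelled Grade 3 or higher. The MAD dose-interruption text in section 3.3 reads "Serum AST or ALT are increased to" the same level with the same grade label, so there either enzyme is enough.

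The SAP changes none of this.

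**The concern.** The sponsor chose to stop on one subject for repeated hypoglycaemia, a risk tied to the drug's mechanism. The non-serious limit reverses the expected order, because repeated events in one subject lose the one-subject stop once they become serious. It also fits poorly with the Grade 3 or higher wording: section 8.7 describes Grade 4 as life-threatening, and section 8.5 makes life-threatening events serious, so the worst events drop out.

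The liver wording leaves a subject with, say, ALT at 6xULN and AST at 3xULN undecided. In the MAD part that subject could have dosing interrupted, yet it is unclear whether the case counts as dose-limiting for the cohort. If Table 7 is also used to count dose-limiting adverse events, a primary endpoint in section 2.2.1, the same uncertainty carries over.

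**Working it through.** **1. The plan's own figure.** Table 10 (protocol section 9.1) gives the chance of two or more SAEs among 6 or 8 active subjects. The formula is P(X≥2) = 1 − (1−p)^n − n·p·(1−p)^(n−1). At p = 0.10 it gives 0.114 for n = 6 and 0.187 for n = 8 (stated 0.11 and 0.19). All 14 cells agree within 0.02. The only difference at two decimals is p = 0.33, n = 6 (0.642 against 0.65), and p = 1/3 gives 0.649. The table fits a reading in which SAEs are judged on two or more per cohort.

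**2. The wording applied to cases.**

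| Active subjects with Grade 3 or higher hypoglycaemia | Numeric stop? |
|---|---|
| One subject, two non-serious events | Yes, one-subject exception |
| One subject, one serious and one non-serious | No, only one event qualifies |
| One subject, two serious | No, neither event qualifies |
| Two subjects, one serious event each | Yes, taken to meet the two-subject rule |

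Removing the limit alone would leave a gap. Table 7 needs glucose below 40 mg/dL. Section 7.6.1 accepts a severe event at 49 mg/dL or below, or with glucose unmeasured, and the SAE definition in section 8.5 has no glucose level. Two serious events at 45 mg/dL would still miss the row.

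**3. Size, hypoglycaemia.** The documents give no rates, so all of these are assumed. Subjects are treated as independent.
- p1: share of active subjects with at least one serious event.
- p2: share, within p1, with two or more qualifying events that the present exception misses.
- As written: 1 − (1−p1)^n − n·p1·(1−p1)^(n−1).
- With serious events counted: 1 − (1−p1)^n − n·(p1−p2)·(1−p1)^(n−1).
- Added chance: n·p2·(1−p1)^(n−1).

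For n = 8, p1 = 5%, p2 = 1%: as written, 1 − 0.66342 − 0.27933 = 0.057; after the edit, 1 − 0.66342 − 0.22347 = 0.113. The added chance is 0.056.

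| p1 | n = 8: as written | n = 8: p2 = 10% to 50% of p1 | n = 6: as written | n = 6: p2 = 10% to 50% of p1 |
|---|---|---|---|---|
| 2% | 0.010 | 0.024 to 0.080 | 0.006 | 0.017 to 0.060 |
| 5% | 0.057 | 0.085 to 0.197 | 0.033 | 0.056 to 0.149 |
| 10% | 0.187 | 0.225 to 0.378 | 0.114 | 0.150 to 0.291 |

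Across the grid the added chance is about 0.01 to 0.19. These are upper bounds for the rates shown, because subjects with only non-serious repeats are left out and they stop escalation under either wording. If a share q of subjects has only non-serious repeats, the added chance becomes n·p2·(1−p1−q)^(n−1). For n = 8, p1 = 5%, p2 = 1%, it falls from 0.056 (q = 0) to 0.038 (q = 5%) and 0.026 (q = 10%).

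**4. Size, liver.** This is the chance of two or more qualifying subjects, with 25% to 75% of affected subjects assumed to have both enzymes raised.

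| Either-enzyme rate | n = 8: either | n = 8: both | n = 6: either | n = 6: both |
|---|---|---|---|---|
| 5% | 0.057 | 0.004 to 0.034 | 0.033 | 0.002 to 0.019 |
| 10% | 0.187 | 0.016 to 0.116 | 0.114 | 0.009 to 0.069 |

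If both enzymes always rise together, the gap is zero. The table covers the Table 7 row alone, not the organ-class part of the main rule.

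**The case against.** The strongest reply is that judgement already covers these cases. Section 3.3 requires a favourable review before each escalation, bars the sponsor from overruling an investigator who decides to stop, and lets the SAD part halt on other findings. It also ends escalation for an intolerable SAD dose or when the MAD safety limit is reached. Table 7 has an open-ended row. Section 3.1 holds the rest of a SAD cohort if either of the first two subjects shows acute toxicity within 24 hours, although that covers early events only. This stands: two serious hypoglycaemic events in one subject would be hard to call well tolerated. It does not explain why the numeric stop should lapse just when events become serious.

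The main rule is not mechanical either. It turns on similarity and clinical significance, and Table 7 exempts events judged unrelated. That also stands, so calling these stops automatic would go too far.

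On the liver row, the either-enzyme reading is the more natural one given the interruption text. The organ-class part of the main rule may also already capture two subjects with single-enzyme rises, because section 8.4 makes ALT or AST at 3xULN or above an adverse event and section 8.7 calls Grade 3 severe. Its tie to the miscited table leaves this open. SAP section 10.2.2.4 tabulates the elevations in any case.

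Severe and serious are different things, as section 8.7 says, so section 7.6.1 does not by itself show serious events at 45 mg/dL. It shows only that the glucose level in Table 7 is narrower than the protocol's own idea of a severe event.

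**Conclusion.** Both wording defects are real and sit in the current protocol text. The hypoglycaemia exception gives repeated serious events in one subject a weaker numeric stop than repeated non-serious ones. The liver row contradicts itself.

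A reader might infer more than the documents support:
- That escalation could go ahead unchecked after serious hypoglycaemia. It could not; the review and the discretionary stops still apply.
- That a single-enzyme rise does not count towards the cohort stop. The row is ambiguous and does not settle this.
- That the loss is as large as the difference between a one-subject and a two-subject rule, for example 0.57 against 0.19 at 10% and n = 8. That comparison treats every affected subject as a repeater, and so ignores subjects with one serious event, who already count towards the two-subject rule.

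The better figure is an added chance of at most about 0.06 for n = 8, with 5% having a serious event and 1% a missed repeat. It rests entirely on assumed rates. The practical effect on escalation here is likely small. The top SAD dose, 6 mg/kg, has been given (protocol section 1.3.3), the remaining planned SAD cohort is 1 mg/kg IV, and SAP section 3 lists final MAD cohorts of 50, 75 and 150 mg, with higher doses judged unnecessary.

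**What to change.** 1. In both stopping bullets of section 3.3 and in the Table 7 hypoglycaemia row, replace "which do not meet SAE criteria" with 'whether or not they meet SAE criteria'. Add that a hypoglycaemic event meeting SAE criteria counts even if glucose was not below 40 mg/dL or was not measured. The second part is a small new criterion, not pure wording. A single serious event would still fall under the two-subject rule and the review, so the edit addresses repeated events only.
2. In the Table 7 liver row delete 'both', so that either enzyme above 5xULN qualifies, as in the interruption text. Use the same reading if Table 7 is used to count dose-limiting adverse events.
3. In the two stopping bullets change the reference from Table 3 to Table 7.

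The cost is a handful of phrases in sections 3.3 and 3.3.1, with no new assessments. The price is a somewhat higher chance of a numeric stop (0.113 instead of 0.057 in the worked example, as an upper-bound increase), and single-enzyme rises would clearly count towards the cohort stop.

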4. SUBJECT SELECTION

This study can fulfill its objectives only if appropriate subjects are enrolled. The following eligibility criteria are designed to select subjects for whom protocol treatment is considered appropriate. All relevant medical and non-medical conditions should be taken into consideration when deciding whether this protocol is suitable for a particular subject.

4.1. Inclusion Criteria

Subject eligibility should be reviewed and documented by an appropriately qualified member of the investigator's study team before subjects are included in the study.

Subjects must meet all of the following inclusion criteria to be eligible for enrollment into the study:

1. Men and women of *non-childbearing potential* between the ages of 18 and 70 years, inclusive, with type 2 diabetes mellitus. Women subjects of *non-childbearing potential* *must meet* at least one of the following criteria:
 - a. Achieved postmenopausal status, defined as: cessation of regular menses for at least 12 consecutive months with no alternative pathological or physiological cause; and have a serum follicular stimulating hormone (FSH) level within the laboratory's reference range for postmenopausal women;
 - b. Have undergone a documented hysterectomy and/or bilateral oophorectomy;
 - c. Have medically confirmed ovarian failure.

All other women subjects (including women with tubal ligations and women that do NOT have a documented hysterectomy, bilateral oophorectomy and/or ovarian failure) will be considered to be of childbearing potential, and are not eligible for the study.

2. Body Mass Index (BMI) of 22.0 to 40.0 kg/m²; and a total body weight >50 kg (110 lbs) and ≤150 kg, and ≤125 kg for Cohort 4 (SAD).
3. Subjects on stable metformin dose x 30 days prior to the first Screening visit and will remain on stable dose throughout the study.
 - SAD Cohorts: metformin dose ≥1500 mg daily
 - MAD Cohorts: metformin dose ≥1000 mg daily
4. HbA1c 7.0 - 10.0% (SAD Cohorts) or HbA1c 6.5-10.5% (MAD Cohorts) inclusive at Screening.
5. Fasting C-peptide >1.21 ng/mL (SAD cohorts) or ≥0.8 ng/mL (MAD cohorts) at Screening.
6. Evidence of a personally signed and dated informed consent document indicating that the subject (or a legal representative) has been informed of all pertinent aspects of the study.
7. Subjects who are willing and able to comply with all scheduled visits, treatment plan, laboratory tests, and other study procedures.

4.2. Exclusion Criteria

Subjects presenting with any of the following will not be included in the study:

Exclusions for General Health

1. History of type 1 diabetes mellitus
2. Evidence or history of diabetic complications with significant end-organ damage including but not limited to:
 - proliferative retinopathy;
 - macular edema;
 - diabetic nephropathy;
 - severe neuropathy;
 - neuropathic ulcers.
3. History of chronic pancreatitis or at high risk for pancreatitis including but not limited to gall bladder disease, hypertriglyceridemia, hypercalcemia, or alcohol abuse.
4. Risk of pancreatic neuroendocrine neoplasm including but not limited to personal or family history of islet cell tumor, multiple endocrine neoplasia 1 (MEN) syndrome, Von Hippel-Lindau syndrome or neurofibromatosis.
5. History of severe hypoglycemia (ie, requiring assistance) or hypoglycemia unawareness within 1 year of randomization.
6. Poorly controlled hypertension (systolic blood pressure >160 mm Hg or a diastolic blood pressure >90 mm Hg, even with treatment). Subjects who have hypertension and are controlled on stable dosages of anti-hypertensive medications can be included.
7. History of a cardiovascular or cerebrovascular event or procedure (eg, MI, stroke, stent) within one year of randomization.
8. Heart failure, NY Class 2, 3, 4.
9. Past or current history of alcoholism or drug addiction according to Diagnostic Statistical Manual (DSM) IV criteria, or use of any recreational drugs within 12 months prior to the first Screening visit.
10. History of diabetic ketoacidosis (DKA), hyperosmolar coma, or lactic acidosis.

11. History of cancer within the last 5 years (except for cutaneous basal cell or squamous cell cancer resolved by excision).
12. Regular alcohol consumption >2 drinks/day (1 drink = 5 ounces [150 mL] of wine or 12 ounces [360 mL] of beer or 1.5 ounces [45 mL] of hard liquor) within 30 days prior to the first Screening visit.
13. Blood donation (excluding plasma donations) of approximately 1 pint (500 mL) or more within 56 days prior to dosing or plans to donate during the conduct of the study.
14. Evidence or history of clinically significant hematological, renal, endocrine, pulmonary, gastrointestinal, cardiovascular, immunologic, hepatic, psychiatric, neurologic, or allergic disease (exception: untreated, asymptomatic, seasonal allergies at the time of dosing allowed) unless deemed not clinically significant by the Investigator and Sponsor.

Exclusions Related to Medications

15. Treatment with anti-diabetic therapies other than metformin within 4 weeks of Screening (8 weeks for thiazolidinediones).
16. Change in dietary supplement or herbal medicine within 2 weeks of Screening.
17. Contraindication to metformin therapy, per the metformin label.
18. Known hypersensitivity to metformin.
19. Subject participating in or expecting to participate in other clinical trials.
20. Subjects on chronic systemic corticosteroids [ie, oral, IV or intramuscular (IM)].
21. Treatment with a marketed or investigational monoclonal antibody within 6 months or 5 half-lives (whichever is longer) of Day -1. (Subjects that participated in the SAD portion of the study may participate in the MAD portion of the study with dosing for the MAD starting 6 months after Day 1 in the SAD study [ie, count from day of when single dose administered in SAD] provided they are ADA negative and their last measured glucagon levels during the SAD portion are not above 3X baseline (baseline: pre-dose value prior to dosing in the SAD portion of the study).
22. History of allergic or anaphylactic reaction to any therapeutic or diagnostic monoclonal antibody (IgG protein) or molecules made of components of monoclonal antibodies (eg, Enbrel® which is the Fc portion of an antibody or Lucentis® which is a Fab).
23. History of sensitivity to heparin or heparin-induced thrombocytopenia (if heparin is used to flush intravenous catheters) or known or suspected hypersensitivity to any of the components of drug product.

24. Treatment with an investigational small molecule drug within 90 days or 5 half-lives of Day -1, whichever is longer.

25. Need for radiologic studies involving use of intravascular iodinated contrast materials.

Exclusions for abnormal screening labs or procedures:

Abnormal labs or procedures may be repeated once for confirmation at the discretion of the Investigator (repeat only the abnormal test, not entire panel).

26. FPG <60 or >250 mg/dL.

27. Creatinine clearance \leq 60 mL/min/1.73m² based on the MDRD.

28. Fasting triglycerides >400 mg/dL.

29. Hemoglobin <11 g/dL in females; <12 g/dL in males .

30. Positive anti-drug antibody (ADA) test for PF-06293620, if the subject previously participated in SAD portion (MAD portion of the study only).

31. Positive human immunodeficiency virus (HIV) antibody, hepatitis B surface antigen (HBsAg), hepatitis B core antibody (HBcAb), or hepatitis C antibody tests indicative of present or prior infection.

NOTE: If a subject tests negative for HBsAg, but positive for HBcAb, the subject will be considered eligible if the subject tests positive for antibody to HB surface antigen (HBsAb or anti-Hbs).

32. AST or ALT >2xULN at Screening. If the subject participated in SAD, no ALT or AST elevation \geq 3xULN during the SAD.

33. Direct bilirubin >ULN.

34. TSH < LLN or > ULN.

35. Platelets < LLN or >450,000 U/uL.

36. Creatine kinase >2xULN.

37. Positive urine drug (illicit) screen (positive drug screen for prescription drugs, eg benzodiazepines, allowed if approved by Sponsor).

38. 12 lead ECG demonstrating QTc >450 msec or a QRS interval >120 msec at Screening. If QTc exceeds 450 msec, or QRS exceeds 120 msec, the ECG should be repeated two more times and the average of the three QTc or QRS values should be used to determine the subject's eligibility.

39. Any abnormal hematology values, clinical chemistries, urinalysis, or ECGs judged by the Investigator or Sponsor as clinically significant.

Other Exclusions:

40. Pregnant or breast-feeding women.

41. Men who are unwilling or unable to use a highly effective method of contraception as outlined in this protocol for the duration of the study and for at least 60 days after the last dose of investigational product.

42. Unwilling or unable to comply with the Lifestyle guidelines described in this protocol.

43. Other severe acute or chronic medical or psychiatric condition or laboratory abnormality that may increase the risk associated with study participation or investigational product administration or may interfere with the interpretation of study results and, in the judgment of the investigator, would make the subject inappropriate for entry into this study.

44. Subjects who are investigational site staff members directly involved in the conduct of the study and their family members, site staff members otherwise supervised by the Investigator, or subjects who are Pfizer employees directly involved in the conduct of the study.

